6.6.5 Management of Thromboembolic Events

Participants should be advised to pay attention to symptoms suggestive of venous thromboembolic events, which include acute onset of shortness of breath, dyspnea, chest pain, cough, hemoptysis, tachypnea, tachycardia, cyanosis, deep vein thrombosis signs including lower-extremity swelling, redness, and warmth to touch or tenderness. In case any of these symptoms appear, participants should be instructed to report such symptoms promptly to the treating physician. If a thromboembolic event is confirmed, instructions contained in [Table 3](#) should be followed. Appropriate supportive care should be provided together with close monitoring. If a participant experiences a Grade 3 or life-threatening (Grade 4) thromboembolic reaction, including pulmonary embolism, lenvatinib must be discontinued.

Arterial thromboembolic events (eg, new onset, worsening, or unstable angina, myocardial infarction, transient ischemic attack, and cerebrovascular accident) of any grade require discontinuation of lenvatinib.

6.6.6 Management of Posterior Reversible Encephalopathy Syndrome (PRES)/Reversible Posterior Leukoencephalopathy Syndrome (RPLS)

PRES/RPLS is a neurological disorder that can present with headache, seizure, lethargy, confusion, altered mental function, blindness, and other visual or neurologic disturbances. Mild to severe hypertension may be present. An MRI is necessary to confirm the diagnosis of PRES/RPLS. The key diagnostic imaging feature for PRES, which can differentiate this entity from disease progression secondary to CNS tumors, is based on imaging evidence of new, bilateral/symmetric vasogenic edema without correlation with the location of the tumor/surgical cavity. Appropriate measures should be taken to control BP (see Section 6.6.1), and neurologic consultation is advised. In participants with signs or symptoms of PRES/RPLS, dose modification guidelines as per [Table 3](#) should be followed.

6.6.7 Management of Hepatotoxicity

Regular monitoring of liver function tests (ALT, AST, and bilirubin levels) should be conducted as detailed in the SoA ([Table 1](#)) and as clinically indicated. If signs/symptoms indicating liver injury occur, dose modification guidelines contained in [Table 3](#) should be followed. Appropriate supportive care should be provided together with close monitoring. If hepatic failure (any grade per CTCAE v5) occurs, lenvatinib must be discontinued.

6.6.8 Management of Hypocalcemia

Serum calcium should be monitored monthly per the SoA (Table 1). Corrected serum calcium should be used to assess the grade of hypocalcemia per CTCAE v5.0, using the following formula:

$$\text{Corrected calcium} = (4 - \text{serum albumin in g/dL}) \times 0.8 + \text{serum calcium}$$

The formula is not applicable when serum albumin concentration is normal (>4 g/dL); in such situations, the total (uncorrected) serum calcium should be used instead.

Hypocalcemia should be treated per institutional guidelines (eg, using appropriate calcium, magnesium, and vitamin D supplementation) until resolution.

6.6.9 Management of Hemorrhage

Dose modification guidelines in Table 3 for lenvatinib-related AEs should be followed for the management of hemorrhage. Lenvatinib should either be resumed at a reduced dose or discontinued, depending on the severity and persistence of hemorrhage.

6.6.10 Management of Fistula Formation and Gastrointestinal Perforation

Lenvatinib should be discontinued in any participants who develop Grade 4 fistula (GI or non-GI), or GI perforation of any grade.

6.6.11 Management of QT Prolongation

Lenvatinib should be withheld in the event of development of QT interval prolongation greater than 500 msec. Lenvatinib should be resumed at a reduced dose when QTc prolongation is resolved to <480 msec or baseline. Monitor potassium, calcium and magnesium, and replenish as appropriate.

6.6.12 Management of Osteonecrosis of the Jaw

Perform an oral examination prior to treatment with lenvatinib and periodically during lenvatinib treatment. Advise participants regarding good oral hygiene practices. Avoid invasive dental procedures, if possible, while on lenvatinib treatment, particularly in participants at higher risk. For participants requiring invasive dental procedures, discontinuation of bisphosphonate treatment may reduce the risk of ONJ. Withhold lenvatinib if ONJ develops and restart based on clinical judgement of adequate resolution (See Section 6.7)

6.7 Other Allowed Dose Interruptions for Lenvatinib

If the participant is receiving treatment with lenvatinib and requires surgery during the study, the stop time and restart time of lenvatinib should be as follows:

- For minor procedures: stop lenvatinib at least 2 days before the procedure and restart it at least **2 days after, once there is evidence of adequate healing and no risk of bleeding.**
- For major procedures: stop lenvatinib at least 1 week (5 half-lives) prior to surgery and then restart it at least 2 weeks after, once there is evidence of adequate healing and no risk of bleeding.
- For scheduled dental surgery or invasive dental procedures, stop lenvatinib for at least 1 week before the procedure, then restart lenvatinib when deemed clinically appropriate.

6.8 Intervention After the End of the Study

There is no study-specified intervention after the end of the study.

6.9 Clinical Supplies Disclosure

This study is open-label; therefore, the participant, the study site personnel, the Sponsor, and/or designee are not blinded. Study intervention (name, strength, or potency) is included in the label text; random code/disclosure envelopes or lists are not provided.

6.10 Standard Policies

Not applicable.

6.10.1 Study Site Retention Samples

Not applicable.

7 DISCONTINUATION OF STUDY INTERVENTION AND PARTICIPANT WITHDRAWAL

7.1 Discontinuation of Study Intervention

Discontinuation of study intervention does not represent withdrawal from the study.

As certain data on clinical events beyond study intervention discontinuation may be important to the study, they must be collected through the participant's last scheduled follow-up, even if the participant has discontinued study intervention. Therefore, all participants who discontinue study intervention prior to completion of study treatment will still continue to participate in the study as specified in Section 1.3 and Section 8.11.4.

Participants may discontinue study intervention at any time for any reason or be discontinued from the study intervention at the discretion of the investigator should any untoward effect

occur. In addition, a participant may be discontinued from study intervention by the investigator or the Sponsor if study intervention is inappropriate, the study plan is violated, or for administrative and/or other safety reasons. Specific details regarding procedures to be performed at study intervention discontinuation are provided in Section 1.3 and Section 8.11.4.

A participant must be discontinued from study intervention but continue to be monitored in the study for any of the following reasons:

- The participant or participant's legally acceptable representative requests to discontinue study intervention.
- The participant interrupts study intervention administration for more than 28 consecutive days.

Note: Exceptions can be made with Sponsor consultation.

- The participant has a medical condition or personal circumstance, which, in the opinion of the investigator and/or Sponsor, placed the participant at unnecessary risk from continued administration of study intervention.
- The participant has a confirmed positive serum pregnancy test.
- The participant experiences objective progression of disease (according to RECIST 1.1 or RANO criteria, for HGG).
- The participant exhibits no clinical benefit (in the opinion of the investigator).
- The participant experiences unacceptable toxicity leading to withdrawal from the study.
- The study is terminated by the Sponsor.
- Administrative reasons.

For participants who are discontinued from study intervention but continue to be monitored in the study, all visits and procedures, as outlined in the SoA, should be completed.

Discontinuation from study intervention is "permanent." Once a participant is discontinued from study intervention, he/she shall not be allowed to restart study intervention.

7.2 Participant Withdrawal From the Study

A participant must be withdrawn from the study if the participant or participant's legally acceptable representative withdraws consent from the study.

If a participant withdraws from the study, they will no longer receive study intervention or be followed at scheduled protocol visits.

Specific details regarding procedures to be performed at the time of withdrawal from the study, are outlined in Section 8. The procedures to be performed should a participant repeatedly fail to return for scheduled visits and/or if the study site is unable to contact the participant are outlined in Section 7.3.

7.3 Lost to Follow-up

If a participant fails to return to the clinic for a required study visit and/or if the site is unable to contact the participant, the following procedures are to be performed:

- The site must attempt to contact the participant and reschedule the missed visit. If the participant is contacted, the participant should be counseled on the importance of maintaining the protocol-specified visit schedule.
- The investigator or designee must make every effort to regain contact with the participant at each missed visit (eg, telephone calls and/or a certified letter to the participant's last known mailing address or locally equivalent methods). These contact attempts should be documented in the participant's medical record.
- Note: A participant is not considered lost to follow-up until the last scheduled visit for the individual participant. The missing data for the participant will be managed via the prespecified statistical data handling and analysis guidelines.

8 STUDY ASSESSMENTS AND PROCEDURES

- Study procedures and their timing are summarized in the SoA.
- Adherence to the study design requirements, including those specified in the SoA, is essential and required for study conduct.
- The investigator is responsible for ensuring that procedures are conducted by appropriately qualified (by education, training, and experience) staff. Delegation of study site personnel responsibilities will be documented in the Investigator Trial File Binder (or equivalent).
- All study-related medical or dental decisions must be made by an investigator who is a qualified physician.
- All screening evaluations must be completed and reviewed to confirm that potential participants meet all eligibility criteria. The investigator will maintain a screening log to record details of all participants screened and to confirm eligibility or record reasons for screening failure, as applicable.
- Procedures conducted as part of the participant's routine clinical management (eg, blood count) and obtained before signing of ICF may be utilized for screening or baseline purposes provided the procedure met the protocol-specified criteria and were performed within the time frame defined in the SoA.

- Additional evaluations/testing may be deemed necessary by the investigator and or the Sponsor for reasons related to participant safety. In some cases, such evaluation/testing may be potentially sensitive in nature (eg, HIV, Hepatitis C), and thus local regulations may require that additional informed consent, and assent if applicable, be obtained from the participant. In these cases, such evaluations/testing will be performed in accordance with those regulations.

The maximum amount of blood collected from each participant over the duration of the study will be provided in the laboratory manual. Refer to Appendix 7 for country-specific requirements.

Repeat or unscheduled samples may be taken for safety reasons or for technical issues with the samples.

8.1 Administrative and General Procedures

8.1.1 Informed Consent/Assent

The investigator or medically qualified designee (consistent with local requirements) must obtain documented informed consent, and assent if applicable, from each potential participant or their legally acceptable representative prior to participating in this clinical study. If there are changes to the participant's status during the study (eg, health or age of majority requirements), the investigator or medically qualified designee must ensure the appropriate documented informed consent/assent is in place.

8.1.1.1 General Informed Consent/Assent

Informed consent/assent given by the participant or their legally acceptable representative must be documented on a consent/assent form. The form must include the study protocol number, study protocol title, dated signature, and agreement of the participant (or his/her legally acceptable representative) and of the person conducting the consent discussion.

A copy of the signed and dated informed consent/assent form should be given to the participant (or their legally acceptable representative) before participation in the study.

The initial informed consent/assent form, any subsequent revised informed consent/assent form, and any written information provided to the participant must receive the IRB/IEC's approval/favorable opinion in advance of use. The participant or his/her legally acceptable representative should be informed in a timely manner if new information becomes available that may be relevant to the participant's willingness to continue participation in the study. The communication of this information will be provided and documented via a revised consent/assent form or addendum to the original consent/assent form that captures the participant's or the participant's legally acceptable representative's dated signature.

Specifics about the study and the study population are to be included in the study informed consent/assent form.

Informed consent will adhere to IRB/IEC requirements, applicable laws and regulations, and Sponsor requirements. The assent, as applicable will adhere to IRB/IEC requirements, applicable laws and regulations and Sponsor requirements.

8.1.2 Inclusion/Exclusion Criteria

All inclusion and exclusion criteria will be reviewed by the investigator, who is a qualified physician, to ensure that the participant qualifies for the study.

8.1.3 Participant Identification Card

All participants will be given a participant identification card identifying them as participants in a research study. The card will contain study site contact information (including direct telephone numbers) to be used in the event of an emergency. The investigator or qualified designee will provide the participant with a participant identification card immediately after the participant provides documented informed consent/assent. At the time of intervention allocation, site personnel will add the treatment/allocation number to the participant identification card.

The participant identification card also contains contact information for the emergency unblinding call center so that a healthcare provider can obtain information about study intervention in emergency situations where the investigator is not available.

8.1.4 Medical History

A medical and surgical history will be obtained by the investigator or qualified designee. The medical and surgical history will collect all active conditions and any condition that is considered to be clinically significant by the investigator. Details regarding the disease for which the participant has enrolled in this study will be recorded separately and not listed as medical history.

8.1.5 Prior and Concomitant Medications Review

8.1.5.1 Prior Medications

The investigator or qualified designee will review prior medication use, including any protocol-specified washout requirement, and record prior medication taken by the participant within 30 days before the first dose of study intervention. Treatment for the disease for which the participant has enrolled in this study will be recorded separately and will not be listed as a prior medication.

8.1.5.2 Concomitant Medications

The investigator or qualified designee will record medication, if any, taken by the participant during the study. Concomitant medications will be recorded for 30 days after the last dose of study intervention.

8.1.6 Assignment of Screening Number

All consented participants will be given a unique screening number that will be used to identify the participant for all procedures that occur prior to intervention allocation. Each participant will be assigned only 1 screening number. Screening numbers must not be re-used for different participants.

Any participant who is screened multiple times will retain the original screening number assigned at the initial screening visit. Specific details on the screening/rescreening visit requirements are provided in Section 8.11.1.

8.1.7 Assignment of Treatment/Allocation Number

All eligible participants will be allocated, by nonrandom assignment, and will receive a treatment/allocation number. The treatment/allocation number identifies the participant for all procedures occurring after treatment allocation. Once a treatment/allocation number is assigned to a participant, it can never be re-assigned to another participant.

A single participant cannot be assigned more than 1 treatment/allocation number.

8.1.8 Study Intervention Administration

Lenvatinib may be taken at home except on C1D1, C1D15, and C2D1; on these days lenvatinib will be taken in the clinic. An extemporaneous suspension of lenvatinib capsules should be used for participants unable to swallow capsules, as detailed in the Pharmacy Manual. Refer to Section 8.1.8.1 for further details.

Before dose administration on Day 1 of each cycle and prior to a change in dose due to dose reduction, the amount of lenvatinib needed for each participant must be calculated as follows:

$$\text{Scheduled dose (mg/m}^2\text{)} \times \text{BSA (m}^2\text{)} = \text{lenvatinib dose (mg)}$$

BSA will be calculated using the method that is accepted and customarily used by the clinical site. BSA must be calculated on Day 1 of each cycle based on the participant's current height and body weight and should not be corrected for amputation. The dose should be rounded to the nearest whole number. After adjustment for BSA, the daily dose of lenvatinib should not exceed 24 mg daily.

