6.6 Dose Modification

Lenvatinib dose reduction and interruption for participants who experience lenvatinib-related toxicity will be in accordance with the dose modifications described in [Table 3](#). AEs will be graded using CTCAE v5.0.

Asymptomatic laboratory abnormalities, including Grade ≥ 3 abnormalities (eg, elevations of amylase and lipase) that are not considered clinically relevant by the investigator should be managed per institutional guidelines; continuation of treatment should be discussed with the Sponsor.

Dose reductions will occur in succession based on the previous dose. Each reduction is a 20% reduction from the previous dose. Once the dose has been reduced, it cannot be increased at a later date, unless the dose has been mistakenly decreased; in this situation, Sponsor's approval is required to increase the dose. An interruption of lenvatinib >28 days will require consultation between the investigator and the Sponsor and written documentation of the collaborative decision on participant management.

Table 3 Criteria for Temporary Discontinuation of Study Drug, Dose Reduction, and Resumption of Treatment

Dose Modification Guidelines for Lenvatinib-Related Toxicity		
Treatment-Related Toxicity^{a,b}	Management	Dose Adjustment
Grade 1 or Tolerable Grade 2		
	Continue treatment	No change
Intolerable Grade 2^{c, d} or Grade 3^e		
First occurrence	Interrupt lenvatinib until resolved to Grade 0-1 or tolerable Grade 2	11.2 mg/m ² (or 20% reduction of the starting dose) orally QD (1-level reduction)
Second occurrence (same toxicity or new toxicity)	Interrupt lenvatinib until resolved to Grade 0-1 or tolerable Grade 2	9.0 mg/m ² (or 20% reduction of the previous dose) orally QD (1-level reduction)
Third occurrence (same toxicity or new toxicity)	Interrupt lenvatinib until resolved to Grade 0-1 or tolerable Grade 2	7.2 mg/m ² (or 20% reduction of the previous dose) orally QD (1-level reduction)
Fourth occurrence (same toxicity or new toxicity)	Interrupt lenvatinib	Discuss with Sponsor
Grade 4^f: Discontinue Study Treatment		
Abbreviations: BMI = body mass index; CTC = Common Toxicity Criteria; CTCAE = Common Terminology Criteria for Adverse Events; QD = once daily. Note: For grading, see CTCAE version 5.0. Collect all CTC grades of adverse events, decreasing and increasing grade.		

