Lenvatinib should be withheld in any instances where a participant is at imminent risk to develop a hypertensive crisis or has significant risk factors for severe complications of uncontrolled hypertension (eg, BP \geq 99th percentile [BP \geq 160/100 mm Hg], significant risk factors for cardiac disease, intracerebral hemorrhage, or other significant comorbidities). Once the participant has been on the same antihypertensive medications for at least 48 hours and the BP is controlled, lenvatinib should be resumed as described below.

During the treatment period, participants with systolic BP \geq 99th percentile (BP \geq 160 mm Hg) or diastolic BP \geq 99th percentile (BP \geq 100 mm Hg) must have their BP monitored on Day 15 (or more frequently as clinically indicated) until systolic BP has been $<$ 95th percentile (\leq 150 mm Hg) and diastolic BP has been $<$ 95th percentile (\leq 95 mm Hg) for 2 consecutive treatment cycles. If a repeat event of systolic BP \geq 99th percentile (BP \geq 160 mm Hg) or diastolic BP \geq 99th percentile (BP \geq 100 mm Hg) occurs, the participant must resume the Day 15 evaluation until systolic BP has been $<$ 95th percentile (\leq 150 mm Hg) and diastolic BP has been $<$ 95th percentile (\leq 95 mm Hg) for 2 consecutive treatment cycles.

The following guidelines should be followed for the management of systolic BP \geq 99th percentile (BP \geq 160 mm Hg) or diastolic BP \geq 99th percentile (BP \geq 100 mm Hg) confirmed on repeat measurements after at least 30 minutes:

[figure not shown]
- Continue lenvatinib and institute antihypertensive therapy for participants not already receiving antihypertensive medication.
- For those participants already on antihypertensive medication, the dose of the current agent may be increased, if appropriate, or 1 or more agents of a different class of antihypertensive should be added.
- If systolic BP \geq 99th percentile (BP \geq 160 mm Hg) or diastolic BP \geq 99th percentile (BP \geq 100 mm Hg) persists despite maximal antihypertensive therapy, then lenvatinib administration should be interrupted and restarted at a lower dose QD (1 dose level reduction [20%] as specified in [Table 3](#)) only when systolic BP $<$ 95th percentile (BP \leq 150 mm Hg) and diastolic BP $<$ 95th percentile (BP \leq 95 mm Hg) and the participant has been on a stable dose of antihypertensive medication for at least 48 hours.

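### For participants at the 24 mg cap, the mandatory Section 8.1.8 dose formula conflicts with the 20% reduction rule in Section 6.6; from BSA of about 2.10 m² the first reduction leaves the dose unchanged

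*Combined protocol and SAP*

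**What the plan says.** Three sets of instructions bear on a dose reduction.

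- **Table 3 (Section 6.6)** gives the first reduction as 11.2 mg/m², "or 20% reduction of the starting dose) orally QD (1-level reduction". The second and third rows give 9.0 and 7.2 mg/m², each with a similar alternative: "or 20% reduction of the previous dose) orally QD (1-level reduction".
- **Section 6.6** states the general rule: "Dose reductions will occur in succession based on the previous dose", and "Each reduction is a 20% reduction from the previous dose". It adds: "Once the dose has been reduced, it cannot be increased at a later date, unless the dose has been mistakenly decreased". Section 6.6.2 applies the same step to persistent hypertension, with lenvatinib "interrupted and restarted at a lower dose QD (1 dose level reduction [20%] as specified in" Table 3. Section 6.6.11 says: "Lenvatinib should be resumed at a reduced dose when QTc prolongation is resolved to" below 480 msec or baseline.
- **Section 8.1.8** fixes the calculation. It applies at the start of every cycle and whenever the dose is cut: "prior to a change in dose due to dose reduction, the amount of lenvatinib needed for each participant must be calculated as follows". The formula is the mg/m² level times BSA. The result is rounded to a whole number and may not exceed 24 mg.

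No sentence deals with reductions in a participant whose dose is held at 24 mg, and none defines dose in the 20% rule or the no-increase rule.

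**The concern.** While 14 mg/m² times BSA stays below 24 mg, a 20% cut in the mg/m² level and a 20% cut in the mg taken are the same thing apart from rounding. Above the cap they separate. A participant with BSA 2.0 m² would be due 28 mg at 14 mg/m² but receives 24 mg. Moving to 11.2 mg/m² makes the calculated dose 22.4 mg, so most of the step only removes mg that were never given.

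Table 3 applies after intolerable Grade 2 or Grade 3 toxicity, and Section 6.6.2 uses it when severe hypertension persists despite maximal therapy. On the formula route, a large adolescent or young adult restarts at or near the dose that caused the event. Two participants of equal size with the same toxicity can restart up to 5 mg apart, depending on which instruction the site follows. Table 3 sets out three reductions before the site must consult the sponsor, and one of them can be spent with no change in dose.

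**Working it through.** **Inputs.** Starting level 14 mg/m², cap 24 mg, rounding to the nearest whole mg (Section 8.1.8); reduced levels 11.2, 9.0 and 7.2 mg/m² (Table 3); 20% per step (Section 6.6).

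**The plan's own levels reproduce.** 14 × 0.8 = 11.2; 11.2 × 0.8 = 8.96, printed as 9.0; 9.0 × 0.8 = 7.2. Table 3 contains no arithmetic error.

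**Where the cap binds.** 24/14 = 1.714 m². With rounding, 24 mg is given from 23.5/14 = 1.679 m².

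**Route A, 20% off the mg taken.** 24 × 0.8 = 19.2, so 19 mg; 19 × 0.8 = 15.2, so 15 mg; 15 × 0.8 = 12 mg. BSA plays no part.

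**Route B, the Section 8.1.8 formula.** Dose = min(24, round(11.2 × BSA)). The rounded dose reaches k mg at BSA (k − 0.5)/11.2:

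| BSA (m²) | First reduced dose | Cut from 24 mg | Above route A |
|---|---|---|---|
| 1.679 to 1.741 | 19 mg | 20.8% | 0 mg |
| 1.741 to 1.8304 | 20 mg | 16.7% | 1 mg |
| 1.8304 to 1.920 | 21 mg | 12.5% | 2 mg |
| 1.920 to 2.009 | 22 mg | 8.3% | 3 mg |
| 2.009 to 2.098 | 23 mg | 4.2% | 4 mg |
| 2.098 and above | 24 mg | 0% | 5 mg |

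**Is this only rounding?** The same rounding in uncapped participants gives a benchmark: 1 − round(11.2 × BSA)/round(14 × BSA). From 0.8 to 1.714 m² the first cut is 14.3% to 25.0%. In the smallest children it can be less: 8 to 7 mg (12.5%) at about 0.580 to 0.607 m², and 9 to 8 mg (11.1%) at about 0.670 to 0.679 m². So 12.5% is a size of cut that rounding alone can produce. Cuts of 8.3% or less, from about 1.92 m², lie below anything rounding gives.

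**Full sequences.**

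- Route A: 24, 19, 15, 12 mg; total cut 1 − 12/24 = 50%.
- Route B at 2.0 m²: 24, 22, 18, 14 mg; total cut 1 − 14/24 = 41.7%.
- Route B at 2.1 m²: 24, 24, 19, 15 mg; total cut 1 − 15/24 = 37.5%.

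Between 1.8304 and 2.277 m² the second and third formula steps cut 15.8% to 23.8%, so the shortfall there arises at the first step.

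**Day 1 recalculation.** Suppose a site takes route A and gives 19 mg at BSA 2.0 m². On the next Day 1, Section 8.1.8 calls for the formula again: 11.2 × 2.0 = 22.4, so 22 mg, a rise of 22/19 − 1 = 15.8%. If dose means mg, this breaks the no-increase rule; if dose means the mg/m² level, it does not.

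**Body size.** The documents give no BSA distribution and leave the BSA method to the site. Assuming the Mosteller formula (weight = BSA² × 3600/height), 1.92 m² is about 78 kg at 170 cm or 74 kg at 180 cm; 2.098 m² is about 93 kg or 88 kg.

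**The case against.** The strongest reply is that Section 6.6 already settles the matter. It requires 20% off the previous dose, Section 6.6.2 repeats the 20%, and Section 6.6.11 requires a reduced dose, so an unchanged 24 mg is excluded. On this view the percentage alternative in Table 3 exists for participants at the cap. Part of this stands. A reader might infer that no text governs the choice, and the documents do not support that: there is a 20% rule and there is a mandatory formula. The defect is that they conflict. The reply does not remove the conflict, because 11.2 mg/m² is itself 20% below 14 mg/m². A site following the formula can believe it has satisfied Section 6.6 as well.

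Three further points limit the claim, and all three stand.

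- A reader might infer that the routes differ for every capped participant. They agree at 19 mg up to 1.741 m² and differ by 1 mg up to 1.8304 m².
- A reader might treat the 12.5% cut from 1.8304 m² as abnormal. Whole-mg rounding produces that size of cut in the smallest children.
- A reader might infer that the protocol permits a Day 1 rise after a reduction. The no-increase sentence forbids it if dose means mg; what is missing is the definition.

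Reach is also limited. Section 4.4 records that the EWS and HGG cohorts were not expanded and that enrollment of other solid tumors was discontinued. RMS is capped at 17 evaluable participants, in a disease that Section 2.2.1.1.2 says is diagnosed before age 10 in about two-thirds of cases. The participant must also be large and need a reduction. This lowers the importance without resolving the conflict for anyone still dosed under this text. The Pharmacy Manual, which might address the point, is not among the documents.

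**Conclusion.** The point holds as a conflict between two instructions for capped participants, with dose left undefined. The first formula reduction is clearly short of 20%, beyond what rounding explains, from about 1.92 m² (8.3% or less). From 2.098 m² it is no reduction at all, and there Section 8.1.8 cannot be followed together with Section 6.6.11, or with Sections 6.6 and 6.6.2 if dose means the mg taken. These figures rest only on the printed levels, cap and rounding rule; the weights quoted rest on the Mosteller assumption.

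A reader might infer that many participants are exposed or that the trial's results are affected. The documents support neither: no BSA data are given, the number affected is probably small, and no planned analysis depends on the choice. It is worth correcting because the rule operates after significant toxicity and the correction is short.

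**What to change.** Add to Table 3 and Section 8.1.8: for participants whose dose before the first reduction was the 24 mg maximum, each reduction takes 20% off the mg dose being received, rounded to the nearest whole mg (24 to 19 to 15 to 12 mg); later Day 1 BSA recalculation may lower that dose but may not raise it.

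For all other participants, state that the no-increase rule in Section 6.6 refers to the mg/m² level, so that the reduced level times current BSA continues to apply. Without this, a growing child reduced to 18 mg at 1.60 m² (11.2 × 1.60 = 17.92) could not move to 19 mg at 1.70 m² (11.2 × 1.70 = 19.04) without appearing to break the rule. The Pharmacy Manual should carry the same wording.

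The cost is a short wording change. Sample size and planned analyses are unaffected, and uncapped participants stay on BSA-based dosing. Capped participants above 1.741 m² who need a first reduction receive 1 to 5 mg less than the formula would give, which is the 20% step Section 6.6 sets out.
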